4.1. ENDPOINT DERIVATIONS

- Daily percent time within a glucose target range of 70-180 mg/dL (3.9-10 mmol/L) by CGM will be derived by,

Daily percent time (%) = (Actual number of readings satisfying glucose target range of 70-180 mg/dL (3.9-10 mmol/L) / Total number of readings obtained in 24h period from 12 AM to 12 AM) $\times 100$. (Note: The day (24 hours) will be derived using date and time).

- 8h overnight percent time within a glucose target range of 70-180 mg/dL (3.9-10 mmol/L) by CGM will be derived by,

8h overnight percent time (%) = (Actual number of readings satisfying glucose target range of 70-180 mg/dL (3.9-10 mmol/L) / Total number of readings obtained in 8h overnight period from 12 AM (midnight) to 8 AM) $\times 100$.

- Daily duration (min) and Daily percent time with hypoglycemia at each threshold of <70, <60, and <50 mg/dL (3.9, 3.3, and 2.8 mmol/L, respectively) by CGM will be derived by,

Daily percent time (%) with hypoglycemia <70 mg/dL = (Actual number of readings satisfying glucose level less than 70 mg/dL (3.9 mmol/L) / Total number of readings obtained in 24h period from 12 AM to 12 AM) $\times 100$. (Note: The day (24 hours) will be derived using date and time. Similarly, it will be derived for other glucose thresholds).

Daily duration (min) with hypoglycemia <70 mg/dL: (Actual number of readings satisfying glucose level less than 70 mg/dL (3.9 mmol/L) in 24h period from 12 AM to 12 AM) $\times 5$.

(Note: The day (24 hours) will be derived using date and time. Similarly, it will be derived for other glucose thresholds).

- 8h overnight duration (min) and 8h overnight percent time with hypoglycemia at each threshold of <70, <60, and <50 mg/dL (3.9, 3.3, and 2.8 mmol/L, respectively) by CGM will be derived by,

8h overnight percent time (%) with hypoglycemia <70 mg/dL = (Actual number of readings satisfying glucose level less than 70 mg/dL (3.9 mmol/L) / Total number of readings obtained in 8h overnight period from 12 AM (midnight) to 8 AM) $\times 100$.

(Note: similarly, it will be derived for other glucose thresholds).

8h overnight duration (min) with hypoglycemia <70 mg/dL: (Actual number of readings satisfying glucose level is less than 70 mg/dL (3.9 mmol/L) in 8h overnight period from 12 AM (midnight) to 8 AM) $\times 5$. (Note: similarly, it will be derived for other thresholds).

- Daily hypoglycemia incidence (event rate) at each of the specified glucose thresholds by

CGM will be derived by,

Daily hypoglycemia incidence (event rate) <70 mg/dL = (b) (4)

Daily hypoglycemia incidence (event rate) <60 mg/dL (b) (4)

Daily hypoglycemia incidence (event rate) <50 mg/dL = (b) (4)

- **8h overnight hypoglycemia incidence (event rate) at each of the specified glucose thresholds by CGM will be derived by,**

8h overnight hypoglycemia incidence (event rate) <70 mg/dL (b) (4)

8h overnight hypoglycemia incidence (event rate) <60 mg/dL = (b) (4)

8h overnight hypoglycemia incidence (event rate) <50 mg/dL = (b) (4)

- **The average glucose level by CGM between midnight and 08:00 AM (or nearest pre-breakfast timepoint) will be derived by,**

Average glucose level by CGM between midnight and 08:00 AM = Sum of all actual glucose reading values in same units / Total number of glucose readings obtained between midnight (12 AM) and 8 AM.

- **Daily glucose AOC_{0-24h,<70mg/dL} and AUC_{0-24h,>70mg/dL} at each of the specified glucose thresholds will be derived by,**

The daily (24h period from 12 AM to 12 AM) glucose AOC (area over the curve) less than 70 mg/dL (3.9 mmol/L) and AUC (area under the curve) greater than 70 mg/dL (3.9 mmol/L) will be calculated using Trapezoidal rule,

$$AUC = \int_a^b f(x)dx \approx (b - a) * \frac{f(a) + f(b)}{2}$$

a and b are the fixed timepoints. f(a) and f(b) are the glucose concentration values of the respective timepoints. (Note: AOC will be calculated using the same formula. Similarly, it will be derived for other glucose thresholds). [For detailed example, see section 9.1.1 \(Appendix\)](#)

- **8h overnight glucose AOC_{0-8h,<70mg/dL} and AUC_{0-8h,>70mg/dL} at each of the specified glucose thresholds will be derived by,**

The 8h overnight (12 AM midnight to 8 AM) glucose AOC (area over the curve) less than 70 mg/dL (3.9 mmol/L) and AUC (area under the curve) greater than 70 mg/dL (3.9 mmol/L) will be calculated using Trapezoidal rule,

$$AUC = \int_a^b f(x)dx \approx (b - a) * \frac{f(a) + f(b)}{2}$$

a and b are the fixed timepoints. f(a) and f(b) are the glucose concentration values of the respective timepoints. (Note: AOC will be calculated using the same formula. Similarly, it will be derived for other glucose thresholds). [For detailed example, see section 9.1.1 \(Appendix\)](#)

- **Weekly incidence of hypoglycemia (event rate) at each of the specified glucose thresholds by SMBG will be derived by,**

Weekly incidence of hypoglycemia (event rate) <70 mg/dL = The number of unique, discrete, and non-continuous hypoglycemia events (<70 mg/dL threshold) per week over the evaluable period.

Weekly incidence of hypoglycemia (event rate) <60 mg/dL = The number of unique, discrete, and non-continuous moderate hypoglycemia events (<60 mg/dL threshold) per week over the evaluable period.

Weekly incidence of hypoglycemia (event rate) <50 mg/dL = The number of unique, discrete, and non-continuous severe hypoglycemia events (<50 mg/dL threshold) per week over the evaluable period.

(b) (4)

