4. DEFINITIONS & DERIVATIONS

Baseline: Baseline is defined as the last non-missing value (or aggregate/integrated values in the case of CGM or SMBG) prior to the first administration of the study drug, unless otherwise stated. If the assessment occurs on the same day as the first study drug administration, then the time of assessment should be compared to the time of first dose administration.

Change from Baseline: The change from baseline values will be calculated as post-baseline value minus the baseline value.

$$\text{Percent change from Baseline} = \frac{\text{Post baseline value} - \text{Baseline value}}{\text{Baseline value}} \times 100$$

(b) (4)

(b) (4)

SMBG data entered by the patient into the electronic patient diary cannot be edited retroactively by the patient. It is both the source data and the data record, so correction of potentially spurious values cannot be performed (b) (4)

listing of possible spurious values will be medically reviewed and adjudicated for exclusion from the analysis datasets prior to database lock.

Missing data for CGM or SMBG will otherwise not be imputed since it is collected continuously or semi-continuously.

Treatment-Emergent Adverse Event (TEAE): A TEAE is defined as any clinically significant event that starts or that worsens in severity (intensity or frequency) after the first dose of study drug. For purposes of this study, TEAEs for summary tabulation will be further defined as those events which occur within a period of time through the +42 days follow-up visit after the final dose of study drug. Adverse events with onset after ICF but before first dose of study drug or after last dose of study drug +42 days will be summarized and listed separately from TEAEs.

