6. ANALYSIS POPULATION AND TREATMENT GROUPS

6.1. Analysis Population

ITT Population: All patients who are enrolled into the study.

Safety Population: All patients enrolled in the study who receive at least one dose of study drug.

Per protocol Population: All patients who receive at least 4 weeks of study drug (2 bi-weekly doses), with no major protocol violations. A patient in the Per protocol population may be excluded from one or more specific efficacy analyses (i.e. SMBG-related endpoints or CGM-related endpoints), if they have a major protocol deviation affecting only that endpoint (e.g. non-compliance with SMBG only, or non-compliance with CGM only).

PK Population: All patients who receive study drug and have a sufficient number and quality (biologically plausible) of results.

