7.1.5. Protocol Deviation

Protocol deviations will be identified and classified by ICH category 1 through 5 and as minor or major and Important Protocol Deviations (as defined by ICH) will be summarized using count and percentage by cohort and RZ358 Total, for the Safety Population. A listing of patients with protocol deviations will be presented.

Compliance will be check for CGM & SMBG and below definitions will be used for the same.

CGM (Continuous glucose monitoring)

Percent compliance of CGM data will be defined as $\geq 70\%$ data capture during the overall monitored time during the treatment period, including $\geq 70\%$ data capture during the efficacy evaluable period between last dose of study drug and the Day 14 EOT/Follow-up Visit.

$$CGM\ Compliance\ (%) = \frac{\text{Actual number of 5 minutes interval of CGM readings}}{\text{Expected number of 5 minutes interval of CGM readings}} \times 100$$

Subjects will be considered compliant if the % compliance is calculated to be $\geq 70\%$ by each of the above criteria and compliance rate will be summarized using descriptive statistics. Overall compliance will also be summarized using counts and percentages by categorizing it into compliant and non-compliant.

Note: Data capture is defined as available recordings in the 10-day sensor period.

SMBG (Self-Monitoring of Blood Glucose)

Percent compliance of SMBG data will be defined as $\geq 50\%$ data capture during the overall monitored time during the treatment period, including $\geq 75\%$ data capture during the efficacy evaluable period between the last dose of study drug and the Day 14 EOT/Follow-up Visit.

$$\text{SMBG Compliance (\%)} = \frac{\text{Actual number of SMBG readings}}{\text{Expected number of SMBG readings}} \times 100$$

Subjects will be considered compliant if the % compliance meets each of the above criteria, and compliance rate will be summarized using descriptive statistics. Overall compliance rate will be summarized using counts and percentages by categorizing it into compliant and non-compliant.

(b) (4)

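### Minutes of hypoglycemia by CGM are a raw count of low readings x 5, so change from baseline in duration moves with sensor capture while percent time from the same readings does not

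*SAP*

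**What the plan says.** SAP section 4.1 gives both derivations in the same bullets. Percent time has a denominator, namely the count of readings that the sensor delivered that day: "Daily percent time (%) with hypoglycemia <70 mg/dL = (Actual number of readings satisfying glucose level less than 70 mg/dL (3.9 mmol/L) / Total number". Duration has none: "Daily duration (min) with hypoglycemia <70 mg/dL: (Actual number of readings satisfying glucose level less than 70 mg/dL (3.9 mmol/L) in 24h period", then x 5. The overnight version is built the same way: "8h overnight duration (min) with hypoglycemia <70 mg/dL: (Actual number of readings satisfying glucose level is less than 70 mg/dL" between midnight and 8 AM, then x 5. Both rules carry over to 60 and 50 mg/dL.

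Daily duration and daily percent time together form one secondary endpoint (SAP 5.2). The overnight pair is exploratory (SAP 5.3). Change from baseline is tested within cohort in the ITT and PP populations (SAP 7.1.7.2 and 7.1.7.3).

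On incomplete data:

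- **Compliance (SAP 7.1.5).** A patient is CGM-compliant at 70% or more capture over the treatment period, including 70% or more "data capture during the efficacy evaluable period between last dose of study drug and the Day 14 EOT/Follow-up Visit". The readable limits do not mention baseline.
- **Imputation (SAP 4).** "Missing data for CGM or SMBG will otherwise not be imputed since it is collected continuously or semi-continuously". The table in SAP 7.1.7.4 repeats that nothing is imputed for these endpoints.
- **Populations (SAP 6.1).** "A patient in the Per protocol population may be excluded from one or more specific efficacy analyses (i.e. SMBG-related endpoints or CGM-related endpoints" for a major deviation affecting only that endpoint. The ITT definition has no such provision: "ITT Population: All patients who are enrolled into the study".

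**The concern.** A count of low readings depends on two things: how often glucose was low, and how long the sensor was recording. Percent time removes the second by dividing by readings obtained. Duration keeps it. The two components of one secondary endpoint, computed from the same readings, can therefore show different changes from baseline for a reason unrelated to glucose.

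The change score is where this matters. Baseline comes from the outpatient screening CGM period and end of treatment from the two weeks after the last dose. No readable rule makes capture equal in the two periods. If it is unequal, an apparent gain or loss in minutes can arise with no change in glucose. If it is equal but incomplete, a real change is understated.

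**Working it through.** The plan states no figure to reproduce, so the check is algebra followed by illustration.

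**Inputs from the SAP.** Readings come every 5 minutes (7.1.5, and the x 5 multiplier in 4.1). The expected number is 1440 / 5 = 288 per day and 480 / 5 = 96 per night.

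**Formulas.** Let L be low readings, R readings obtained, T the window (1440 or 480 min) and c = R / (T / 5) the capture fraction.

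- Duration as written: D = 5L.
- Percent time as written: P = 100 L / R.
- Minutes implied by percent time over the full window: M = T x L / R.
- Ratio: D / M = 5R / T = c, for L > 0.

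The shortfall of D against M is 1 - c, the share of readings missing in that window. If L = 0, both are 0 and agree. Enumerating every pair (R, L) with R at least 1, for 288 and for 96 expected readings, gave no exception.

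**One day.** 202 of 288 readings obtained, 20 of them low:

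- D = 20 x 5 = 100 min.
- P = 20 / 202 = 9.9%, so M = 1440 x 20 / 202 = 142.6 min.
- Shortfall = 1 - 100 / 142.6 = 29.9%, equal to 86 / 288.

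**Change from baseline, no drug effect.** Assumptions, none from the documents: readings lost at random, the same capture on every day of a period, and the stated share p of time below 70 mg/dL. Expected duration is then p x T x c.

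| p and window | Capture, baseline then EOT | Duration, baseline then EOT (min) | False change (min) |
|---|---|---|---|
| 10%, day | 95%, 85% | 136.8, 122.4 | -14.4 |
| 10%, day | 85%, 95% | 122.4, 136.8 | +14.4 |
| 10%, day | 95%, 70% | 136.8, 100.8 | -36.0 |
| 4%, day | 95%, 85% | 54.72, 48.96 | -5.8 |
| 10%, night | 95%, 85% | 45.6, 40.8 | -4.8 |

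The 4% row uses the entry minimum for time below 70 mg/dL. Expected percent time does not change in any row.

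**Change from baseline, true halving from 10% to 5%.** The true change is 72 - 144 = -72 min/day.

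- Capture 85% both times: 61.2 - 122.4 = -61.2, shrunk by the 15% missing.
- Capture 95% then 85%: 61.2 - 136.8 = -75.6.
- Capture 85% then 95%: 68.4 - 122.4 = -54.0.

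Figures are in absolute minutes because SAP 7.1.7.2 plans percent change for percent time and SMBG incidence, not for duration.

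**The case against.** The strongest reply is that the SAP does not contradict itself. It never multiplies percent time by 1440 or 480. Applied to observed minutes (R x 5), percent time returns exactly the stated duration, and SAP section 3 describes duration as absolute time. A reader might infer an arithmetic error in section 4.1. There is none: the formulas describe observed minutes and an observed proportion. What stands is that observed minutes are not comparable between periods with different observation time, and a change score needs them to be.

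Redaction also limits the point. Text is blacked out just before the no-imputation sentence in SAP section 4, at the end of 7.1.5 and in appendix 9.1.2, and it may hold a valid-day or baseline capture rule. A reader might infer that the plan has no such rule, and the documents do not support that. Such a rule could limit the gap, but it would remove it only by requiring complete days. The duration formulas themselves are fully readable and contain no rescaling.

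A reader might also infer from the 70% limit that a compliant patient's average duration is 30% too low. The limits apply to the treatment period and the last-dose-to-EOT window, while the shortfall arises within each day or night, so the limit does not fix its size. The note "Note: Data capture is defined as available recordings in the 10-day sensor period" defines capture; it does not move the limits to single sensors.

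Finally, percent time at the same thresholds is reported beside duration in the same populations, compliance is summarized, and Protocol 7.1 says that the study is not powered and that p-values are hypothesis-generating. All of this stands and keeps the consequence small.

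**Conclusion.** The concern holds as a minor one. As written, duration equals percent time x 1440 (or 480) min multiplied by the capture fraction whenever at least one reading is low. That part is exact and needs no assumption. The bias in change from baseline is conditional: it needs capture to differ between baseline and the later period, or to be equal but incomplete, in which case the absolute change shrinks by the share missing. Under the illustrative assumptions, a ten-point difference in capture moves the change by 14.4 min/day at 10% of time below 70 mg/dL, and by 5.8 min/day at 4%.

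A reader might infer that the rule favors the drug. The documents do not support that: they give no capture rates, so the actual size and direction are unknown. If losses depend on glucose, the shortfall against true minutes could differ from these figures. The primary endpoint and all percent-time endpoints are unaffected.

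**What to change.** In SAP section 4.1, define duration at each threshold as (readings below threshold / readings obtained) x 1440 min per day, and x 480 min per night from midnight to 8 AM, averaged over the same days or nights as percent time.

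The cost is a short change to the SAP text and the program, because the denominator is already computed for percent time. There are two downsides. Unobserved minutes are assumed to resemble observed ones, and the SAP should state this beside its no-imputation entry for these endpoints in 7.1.7.4. Duration also becomes percent time expressed in minutes (x 14.4 per day, x 4.8 per night), so its tests add nothing to those on percent time.

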7.1.7.3. Exploratory Endpoints

The exploratory endpoints to measure glycemic control by CGM and SMBG will be evaluated, at each of the specified timepoints, compared to baseline. The analysis of CGM parameters and SMBG

parameters will be performed over the 2-week End of Treatment period after the final dose, compared to baseline. The exploratory endpoints analysis will be conducted in the PP and ITT Populations. The following exploratory endpoints include:

- Average 8h overnight duration (min) and percent time with hypoglycemia at thresholds of <70, <60, and <50 mg/dL (3.9, 3.3, and 2.8 mmol/L, respectively) by CGM
- Average 8h overnight hypoglycemia incidence (event rate) at each of the specified glucose thresholds by CGM
- Average daily and 8h overnight area over and under the glucose curve (AUC, AOC) for each of the specified glucose thresholds by CGM
- Average glucose level between midnight and 8:00 AM (or nearest pre-breakfast time point) by CGM
- Average weekly hypoglycemia incidence (event rate) at each of the specified glucose thresholds of <70, <60, and <50 mg/dL (3.9, 3.3, and 2.8 mmol/L, respectively) by SMBG

Additionally, Average weekly hyperglycemia incidence (event rate) at each of the specified glucose thresholds of >180, >250, and >300 mg/dL (10.0, 13.9 and 16.6 mmol/L, respectively) by SMBG

The derivations of above exploratory endpoints are presented in [section 4.1](#). The exploratory endpoints of actual and change from baseline values will be summarized by visit, cohort and RZ358 Total using descriptive statistics (n, Mean, SD, SE, Median, Minimum, Maximum and 95% CI for Mean). Along with these, First Quartile (Q1) and Third Quartile (Q3) will also be presented for duration (min) parameters. AOC and AUC of above glucose parameters will also be summarized by visit, cohort and RZ358 Total using descriptive statistics (n, Mean, SD, SE, CV (%), Geometric Mean, Geometric CV (%), Median, Minimum, Maximum and 95% CI for Geometric Mean). Within cohort comparative analysis will be performed using paired t test by comparing each post baseline visits with baseline visit, p-value from the test will be reported and analysis will be performed using ITT and PP Populations. Corresponding mean (SD) plots will also be produced for above endpoints to illustrate the descriptive statistics as appropriate.

Comparison of glycemic efficacy of RZ358 by CGM/SMBG endpoints

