9. APPENDIX

9.1.1. AUC and AOC Derivation

[figure not shown]
Daily glucose AOC and AUC at each of the specified glucose thresholds by CGM

The figure below is presented only to show the idea of the calculation of glucose AUC and AOC parameters and the shape of the curve is based on dummy data. The parameters will be calculated using Linear Trapezoidal Rule over the specified time range.

Daily glucose AOC (area over the curve) less than 70 mg/dL (3.9 mmol/L) and AUC (area under the curve) greater than 70 mg/dL (3.9 mmol/L) will be calculated using Trapezoidal rule,

$$AUC/AOC = \int_a^b f(x)dx \approx (b - a) * \frac{f(a) + f(b)}{2}$$

AUC & AOC Example

- From the above figure, the horizontal reference line is the glucose threshold of 70 mg/dL (3.9 mmol/L)
- Area over the curve (AOC) < 70 mg/dL will be calculated as sum of AOC parts (Lavender) using Linear Trapezoidal Rule
- Area under the curve (AUC) > 70 mg/dL will be calculated as sum of AUC parts (Yellow) using Linear Trapezoidal Rule

AUC_{0-t}(mg/dL × Hours) for plasma glucose > 70 mg/dL

From the yellow region of the example figure, the glucose AUC (area under the curve) > 70 mg/dL is calculated as follows:

$$\begin{aligned} \text{AUC}_{0-12h>70\text{mg/dL}} &= [(2-1)(0+60)/2] + [(4-2)(60+30)/2] + [(6-4)(30+0)/2] \\ &= 30 + 90 + 30 \\ &= 150 \frac{\text{mg}}{\text{dL}} \cdot \text{hr} \end{aligned}$$

AOC_{0-t} (mg/dL × Hours) for plasma glucose < 70 mg/dL

From the lavender region of the example figure, the glucose AOC (area over the curve) < 70 mg/dL is calculated as follows:

$$\begin{aligned} \text{AOC}_{0-12h<70\text{mg/dL}} &= [(1-0) (70+0)/2] + [(8-6) (0+20)/2] + [(10-8) (20+50)/2] + [(12-10) (50+60)/2] \\ &= 35 + 20 + 70 + 110 \\ &= 235 \frac{\text{mg}}{\text{dL}} \cdot \text{hr} \end{aligned}$$

[figure not shown]
Similarly, these methods will be used to derive other endpoints, such as 8h overnight glucose AOC and AUC at each of the specified glucose thresholds <70, <60 and <50 mg/dL (3.9, 3.3 and 2.8 mmol/L, respectively) and >70, >60 and >50 mg/dL (3.9, 3.3 and 2.8 mmol/L, respectively) respectively by CGM.

9.1.2. (b) (4)

(b) (4)

(b) (4)

[figure not shown]
(b) (4)

(b) (4)

(b) (4)

(b) (4)

(b) (4)

(b) (4)

(b) (4)

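### SAP 4.1 defines the AUC/AOC trapezoid on raw glucose, while the worked example in 9.1.1 uses distance from the threshold; the example shows the likely intent and 4.1 should be brought into line

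*SAP*

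**What the plan says.** SAP 4.1 (Endpoint Derivations) has two bullets on these areas, one for the 24 h day and one for the overnight window from midnight to 8 AM. Each prints the trapezoid (b - a) × (f(a) + f(b)) / 2 and explains that "f(a) and f(b) are the glucose concentration values of the respective timepoints". Each adds that "AOC will be calculated using the same formula" and that the other thresholds follow in the same way. Neither formula contains a threshold term. Both bullets send the reader to 9.1.1 for a detailed example.

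SAP 9.1.1 (AUC and AOC Derivation) prints the same formula without redefining f. It places a reference line at 70 mg/dL and introduces the first calculation with "From the yellow region of the example figure, the glucose AUC (area under the curve) > 70 mg/dL is calculated as follows". The ordinates it then uses are 0, 60, 30 and 0 for AUC, and 70, 0, 0, 20, 50 and 60 for AOC. The results are 150 and 235 mg/dL·hr. The section closes by extending the method to the overnight window and to the 60 and 50 mg/dL thresholds.

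SAP 7.1.7.3 lists the endpoint as exploratory: "Average daily and 8h overnight area over and under the glucose curve (AUC, AOC) for each of the specified glucose thresholds by CGM". It is summarised by visit and cohort, with geometric means, and compared with baseline in the ITT and PP populations.

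**The concern.** The definition and the example describe different quantities. In a region where glucose is above 70 mg/dL, ordinates of 0, 60 and 30 cannot be glucose concentrations; they make sense only as height above the 70 line. Yet the only sentence that says what f is calls it a concentration.

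The difference matters most for AOC, which is meant to grow with both the depth and the duration of hypoglycaemia. Integrating raw glucose below the threshold rewards duration and penalises depth. A treatment that made episodes shallower without shortening them would then appear to worsen AOC. For AUC, the raw version adds the rectangle of height T under the threshold for all the time spent above it, so the excess over threshold is mixed with time above threshold.

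Two programmers working independently, one from 4.1 and one from 9.1.1, would produce different datasets, and each could point to the SAP. Daily and overnight, AUC and AOC, at three thresholds make 2 × 2 × 3 = 12 parameters that depend on the definition.

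**Working it through.** **Inputs.** The formula and the meaning of f come from SAP 4.1. The times, ordinates and results come from SAP 9.1.1. The example figure is not available in the text reviewed, so the glucose values in step 2 are inferred from the printed ordinates, treating them as distances from 70 mg/dL.

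**1. Reproduce the SAP's figures, with f as distance from 70.**
- AUC: (2-1)(0+60)/2 + (4-2)(60+30)/2 + (6-4)(30+0)/2 = 30 + 90 + 30 = 150.
- AOC: (1-0)(70+0)/2 + (8-6)(0+20)/2 + (10-8)(20+50)/2 + (12-10)(50+60)/2 = 35 + 20 + 70 + 110 = 235.

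Both match, so the arithmetic of the example is correct.

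**2. Infer glucose.** Adding the AUC ordinates to 70 and subtracting the AOC ordinates from 70 gives 0, 70, 130, 100, 70, 50, 20 and 10 mg/dL at 0, 1, 2, 4, 6, 8, 10 and 12 h.

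**3. Apply the 4.1 definition, with f as glucose.**
- Over the example's AUC intervals (1-6 h): 1×(70+130)/2 + 2×(130+100)/2 + 2×(100+70)/2 = 100 + 230 + 170 = 500.
- Over the example's AOC intervals (0-1 h and 6-12 h): 1×(0+70)/2 + 2×(70+50)/2 + 2×(50+20)/2 + 2×(20+10)/2 = 35 + 120 + 70 + 30 = 255.
- Over the whole 0-12 h, since the printed formula has no threshold restriction: 500 + 255 = 755, the same number for AUC and AOC.

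| Reading of f | AUC | AOC |
|---|---|---|
| Distance from 70 (9.1.1) | 150 | 235 |
| Raw glucose, example's intervals | 500 | 255 |
| Raw glucose, full 0-12 h | 755 | 755 |

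**4. Cross-check.** Time above 70 is 5 h, and 500 - 5×70 = 150. Time below 70 is 1 + 6 = 7 h, and 7×70 - 255 = 235. The second identity shows the sign problem: the distance AOC equals T × time below threshold minus the raw area.

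**5. Direction at a fixed time below threshold.** For one flat hour:

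| Glucose, mg/dL | Distance AOC | Raw area |
|---|---|---|
| 65 | 5 | 65 |
| 50 | 20 | 50 |
| 40 | 30 | 40 |

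Lowering the example's last three points by a further 10 mg/dL moves the distance AOC from 235 to 35 + 30 + 90 + 130 = 285, and the raw area from 255 to 35 + 110 + 50 + 10 = 205.

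The whole-window reading behaves the same way. An 8 h night at an assumed 90 mg/dL, with one hour at 65, 50 or 40, gives 7×90 + 65 = 695, 680 or 670.

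**6. Direction when deeper episodes last longer.** Assume a V-shaped episode that falls and rises at 1 mg/dL per minute. With nadir m, the time below 70 is 2(70 - m)/60 h. The raw area is that time × (70 + m)/2, and the distance area is that time × (70 - m)/2.

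| Nadir, mg/dL | Hours below 70 | Distance AOC | Raw area below 70 |
|---|---|---|---|
| 60 | 0.33 | 1.7 | 21.7 |
| 50 | 0.67 | 6.7 | 40.0 |
| 40 | 1.00 | 15.0 | 55.0 |
| 30 | 1.33 | 26.7 | 66.7 |

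Here the raw area rises with depth, because the longer duration outweighs the lower ordinates.

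**The case against.** The best defence is that the SAP resolves the matter itself. Both 4.1 bullets point to 9.1.1, which works the distance method through numerically and carries it over to the overnight window and the other thresholds. The endpoint's name helps too: an area over the curve below 70 cannot sensibly be an integral of glucose down to zero. A programmer who follows the example gets the right quantity. This stands as evidence of intent. It does not remove the conflict, because 9.1.1 is cited only as an example, describes its figure as illustrating the idea on dummy data, and never says that f is a distance.

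Three stronger readings are tempting and are not supported.

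- A reader might infer that, under 4.1, AOC always shrinks as hypoglycaemia deepens. That is so for a fixed time below threshold, and in the whole-window illustration above, but step 6 gives a case where the raw area restricted to time below 70 rises.
- A reader might take 500 and 255 as the result that 4.1 prescribes. They combine 4.1's ordinates with the appendix's intervals; the bare formula over 0-12 h gives 755 for both. All three figures rest on inferred dummy values and say nothing about the size of the gap in trial data.
- A reader might infer an arithmetic error, or a threat to the main efficacy result. The example's sums are correct, and the primary endpoint and all secondary endpoints use other derivations or fasting-challenge data. The protocol also says (7.1) that the study is not powered for significance and that any p-values are hypothesis-generating.

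**Conclusion.** The conflict is real. SAP 4.1 states a derivation rule that, taken literally, does not yield an area over the curve, while 9.1.1 uses the rule that does. On the example the literal rule gives 500 and 255, or 755 for both, against the stated 150 and 235. At a fixed time below threshold it reverses the ranking of severity (65 against 40 raw, where distance gives 5 against 30). Where depth and duration move together, it mixes them with opposite signs.

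This is a defect of specification limited to the exploratory daily and overnight AUC/AOC parameters, and the appendix already shows the likely intent. It is worth correcting because those parameters are tabulated and tested, and the text that defines them should not admit two answers. The conclusion that the passages conflict rests on the printed text alone. The raw-glucose totals also depend on the back-calculated curve, and step 6 depends on the assumed slope.

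**What to change.** In both 4.1 bullets and in 9.1.1, replace the description of f with: for each threshold T (70, 60 and 50 mg/dL), f(t) = max(glucose - T, 0) for AUC and f(t) = max(T - glucose, 0) for AOC. Keep the worked example unchanged; it then agrees with the definition at 150 and 235.

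An optional refinement is to state that an interval in which glucose crosses T between two readings is split at the crossing by linear interpolation. The example meets 70 only at sampled times, so it does not show this case. Whether it matters at 5-minute readings has not been shown.

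The cost is a small text edit in three places of the SAP, plus a check that the program follows it. No new data are needed, and no primary or secondary analysis changes.
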